5.7 Storage

Replagal will be provided by the sponsor (or designee) to the clinical study sites, qualified satellite sites, or patient residences (or other approved location) in a temperature-controlled, monitored container. The vials should be stored in a refrigerator at 2-8°C (36-46°F). A minute amount of fine particulate matter, causing the solution to appear slightly hazy, may be present during storage.

5.8 Investigational Product Accountability and Destruction

The final disposition of all investigational product must be recorded on a patient-by-patient basis. The date and time of administration of the study drug will be documented on the appropriate case report form/electronic case report form (CRF/eCRF).

All used, partially used, and unopened study drug vials must be returned to the sponsor-designated pharmacy.

6 TREATMENT PROTOCOL PROCEDURES

Complete schedules of events for Cohort 1 and Cohort 2 are provided in [Appendix 1](#) and [Appendix 2](#). This protocol is intended to follow the same schedule and assessments as the CFDI protocol, and the safety visits in this protocol are intended to coincide with the biannual or annual visits recommended by the CFDI.

Patients enrolled in this study must be treated in accordance with current Canadian guidelines for the treatment of Fabry disease.

6.1 Eligibility Criteria

Eligibility criteria (provided in [Section 4](#)) will be reviewed, and patient eligibility will be determined prior to the patient receiving the first dose of Replagal.

6.2 Disease and Treatment History

Documentation of diagnosis with Fabry disease will be collected up to 6 months prior to the patient receiving the first dose of Replagal.

6.3 Demographics

Patient demographics, including patient sex, age, and race, will be collected.

6.4 Medical History

A review of the patient's medical history will occur up to 6 months prior to the patient receiving the first dose of Replagal. This review will include a review of body systems, documentation of current procedures, and documentation of current concomitant medication usage. In addition, the patient will be queried on the following:

- Relevant intercurrent illness and chronic disease update
- Medication use and dose (particularly those used to treat Fabry disease)
- Site of prior ERT (ie, hospital, infusion center, doctor's office, home, other)
- Disease-specific review of symptoms, including:
 - Head, neck, and thyroid
 - Eyes, ears, nose, and throat
 - Chest and lungs
 - Heart
 - Lymph nodes
 - Abdomen
 - Anorectal
 - Genitourinary
 - Skin
 - Musculoskeletal

- Endocrine
- Neurological
- Other

6.5 Physical Examination

Complete physical examinations will occur prior to the first dose of Replagal administration and during the biannual or annual safety visits, as applicable. The physical examinations will include assessments of:

- Head, neck, and thyroid
- Eyes, ears, nose, and throat
- Chest and lungs
- Heart
- Lymph nodes
- Abdomen
- Anorectal
- Genitourinary
- Skin
- Musculoskeletal
- Endocrine
- Neurological
- Height (measured at baseline for all patients, and for patients <18 years at baseline, height will also be measured at biannual or annual safety visits until they are ≥ 18 years of age)
- Weight (within 1 month prior to the first Replagal infusion)
- Other

Clinically significant findings from the physical examinations are to be reported as AEs.

6.6 Vital Signs

Vital signs, including blood pressure, pulse, respiratory rate, and temperature, will be measured immediately prior to each infusion and immediately following each infusion (± 10 minutes).

6.7 Blood Tests

Blood will be collected within 6 months prior to the patient receiving the first dose of Replagal and at the biannual or annual safety visits for the following assessments: creatinine, glucose, urea, potassium, sodium, chloride, bicarbonate, and fasting lipids profile.

6.8 Antibody Assessments

Serum samples will be collected for evaluation of anti-agalsidase alfa antibodies within 6 months prior to the patient receiving the first dose of Replagal and at the biannual or annual safety visits, as applicable. Analysis of anti-agalsidase alfa antibodies will be performed using a validated electrochemiluminescent immunoassay following a tiered approach (screening, confirmatory, and titer). Samples that are confirmed positive for the presence of anti-agalsidase alfa antibodies will be further evaluated for the presence of neutralizing antibodies using an enzyme inhibition assay. Sample collection, processing, and shipping instructions will be detailed in the study laboratory manual. This manual is to be provided by the central laboratory.

6.9 Replagal Administration

Patients in Cohort 1 will receive Replagal IV infusions EOW until Replagal is commercially available to the patient or the patient's participation or the study is discontinued.

Patients in Cohort 2 will receive Replagal IV infusions weekly until Replagal is commercially available to the patient or the patient's participation or the study is discontinued.

Replagal administration will occur as described in Section 5.2; home infusions may occur at the discretion of the investigator.

6.10 Adverse Events Assessments

6.10.1 Definitions of Adverse Events and Serious Adverse Events

6.10.1.1 Adverse Event

An AE is any noxious, pathologic, or unintended change in anatomical, physiologic, or metabolic function as indicated by physical signs, symptoms, or laboratory changes occurring in any phase of a clinical study, whether or not considered investigational product-related. This includes an exacerbation of a pre-existing condition.

Adverse events include:

- Worsening (change in nature, severity, or frequency) of conditions present at the onset of the study
- Intercurrent illnesses
- Drug interactions
- Events related to or possibly related to concomitant medications
- Abnormal laboratory values (This includes significant shifts from baseline within the range of normal that the Investigator considers to be clinically important.)
- Clinically significant abnormalities in physical examination, vital signs, and weight

Throughout the study, the investigator must record all AEs on the AE eCRF, regardless of the severity or relationship to investigational product. The investigator should treat patients with

AEs appropriately and observe them at suitable intervals until the events stabilize or resolve. Adverse events may be discovered through observation or examination of the patient, questioning of the patient, complaint by the patient, or abnormal clinical laboratory values.

In addition, AEs may also include laboratory values that become significantly out of range as determined by the investigator or in the opinion of the investigator. In the event of an out-of-range value, the laboratory test should be repeated until it returns to normal or can be explained and the patient's safety is not at risk.

Additional illnesses present at the time when informed consent is obtained are regarded as concomitant illnesses and will be documented on the appropriate pages of the eCRF. Illnesses first occurring or detected during the study, and worsening of a concomitant illness during the study, are to be regarded as AEs and must be documented as such in the eCRF.

6.10.1.2 Infusion-related Reactions

An infusion-related reaction will be defined as an AE that 1) begins either during or within 12 hours after the start of the infusion and 2) is judged as possibly or probably related to study drug. Adverse events that are considered infusion-related reactions will be noted as such in the appropriate field on the eCRF. Other AEs that occur prior to the infusion, along with AEs associated with protocol-defined testing and assessments (laboratory testing and physical examinations) that were performed prior to the infusion, will not be defined as infusion-related reactions. All AEs should be recorded, together with causality assessment.

A list of the most common infusion-related reactions that have been reported in patients with Fabry disease during Replagal infusions is included in the current Replagal IB.

6.10.1.3 Serious Adverse Event

A serious AE (SAE) is any AE occurring at any dose that results in any of the following outcomes:

- Death
- Is life-threatening
- Requires hospitalization
- Requires prolongation of existing hospitalization
- A persistent or significant disability or incapacity
- A congenital anomaly or birth defect

Important medical events that may not result in death, be life-threatening, or require hospitalization may be considered an SAE when, based upon appropriate medical judgment, they may jeopardize the patient and require medical or surgical intervention to prevent one of the outcomes listed in this definition. A life-threatening AE is defined as an AE that placed the patient, in the view of the initial reporter, at immediate risk of death from the AE as it occurred

(ie, it does not include an AE that, had it occurred in a more severe form, might have caused death).

6.10.2 Classification of Adverse Events and Serious Adverse Events

The National Cancer Institute Common Terminology Criteria for Adverse Events (NCI CTCAE) grading scale should be referenced when assessing the severity of an AE. If an AE is not described in the NCI CTCAE, the severity should be recorded based on the scale below. The severity of all AEs/SAEs should be recorded on the appropriate CRF/eCRF page as Grade 1, 2, 3, or 4 corresponding, respectively, to a severity of mild, moderate, severe, or life-threatening ([Table 6-1](#)).

Table 6-1 Adverse Event Severity

Severity	Definition
Grade 1 (Mild)	No limitation of usual activities.
Grade 2 (Moderate)	Some limitation of usual activities.
Grade 3 (Severe)	Inability to carry out usual activities.
Grade 4 (Life-threatening)	Immediate risk of death.

6.10.2.1 Clarification between Serious and Severe

The term severe is often used to describe the intensity (severity) of a specific event (as in mild, moderate, or severe myocardial infarction); the event itself, however, may be of relatively minor medical significance (such as severe headache). This is not the same as “serious,” which is based on the outcome or action criteria usually associated with events that pose a threat to life or functioning. Seriousness (not severity) and causality serve as a guide for defining regulatory reporting obligations.

6.10.3 Relatedness of Adverse Events and Serious Adverse Events

Relationship of an AE or SAE to investigational product is to be determined by the investigator based on the following definitions ([Table 6-2](#)).

Table 6-2 Adverse Event Relatedness

Relationship to Product(s)	Definition
Not Related	Unrelated to investigational product
Possibly Related	A clinical event or laboratory abnormality with a reasonable time sequence to administration of investigational product, but which could also be explained by concurrent disease or other drugs or chemicals.
Probably Related	A clinical event or laboratory abnormality with a reasonable time sequence to administration of investigational product, unlikely to be attributable to concurrent disease or other drugs and chemicals and which follows a clinically reasonable response on de-challenge. The association of the clinical event or laboratory abnormality must also have some biologic plausibility, at least on theoretical grounds.

6.10.4 Procedures for Recording and Reporting Adverse Events

6.10.4.1 Adverse Event Monitoring and Period of Observation

Adverse events will be monitored continuously throughout the study.

For the purposes of this study, the period of observation extends from the time at which the patient, the patient's parent(s), or the patient's legally authorized representative gives informed consent until the patient's final evaluation of the study. For safety purposes, the final evaluation will be defined as the follow-up evaluation performed approximately 30 days after the last dose for patients who complete the study.

If the investigator considers it necessary to report an AE in a study patient after the end of the safety observation period, he or she should contact the sponsor to determine how the AE should be documented and reported.

6.10.4.2 Reporting Serious Adverse Events

Any SAE, regardless of relationship to investigational product, which occurs in a patient after informed consent, should be recorded by the clinical site on an SAE form. The SAE must be completely described on the patient's eCRF, including the judgment of the investigator as to the relationship of the SAE to the investigational product. The investigator will promptly supply all information identified and requested by the sponsor (or contract research organization [CRO]) regarding the SAE.

The investigator must report the SAE to the Shire Pharmacovigilance and Risk Management Department AND to the Shire medical monitor on an SAE form. This form must be completed and FAXED or EMAILED within 24 hours of the investigator's learning of the event to:

Shire Pharmacovigilance and Risk Management Department:
International FAX: PPD [REDACTED] (UK) OR United States and Canada
FAX: PPD [REDACTED]
PPD [REDACTED]
AND
Shire Medical Monitor: PPD [REDACTED], MD, MPH
PPD [REDACTED]
FAX: PPD [REDACTED] (USA)

Any follow-up information must also be completed on an SAE form and faxed or emailed to the same numbers listed above.

In the event of a severe and unexpected, fatal, or life-threatening SAE, the clinical site must contact the Shire medical monitor by telephone; this is in addition to completing and transmitting the SAE form as stated above. The following provides contact information for the Shire medical monitor.

If an SAE is assessed as severe and unexpected or life-threatening, contact:

PPD [REDACTED], MD, MPH

PPD

Shire300 Shire Way, [name]

Telephone: PPD [REDACTED] Fax: PPD [REDACTED] (USA)

Mobile: PPD [REDACTED]

PPD [REDACTED]

The investigator must promptly report all required information to the Institutional Review Board (IRB)/Ethics Committee (EC)/Research Ethics Boards (REB). It is the responsibility of the sponsor to ensure that each investigator receives a copy of any Council for International Organizations of Medical Sciences I/MedWatch report that has been submitted to the appropriate regulatory agencies notifying them of an unexpected related SAE. The investigator or sponsor must ensure that the IRB/EC/REB receives a copy of the report and that a copy is also filed within their study files.

6.11 Management of Infusion-related Adverse Events

If a patient has an IRAE during the infusion of study drug, the investigator or the home infusion nurse should decide, based on his or her clinical judgment, whether the infusion should be slowed or temporarily or permanently discontinued. Mild and transient effects may not require medical treatment or discontinuation of the infusion. Infusion-related AEs that occur post-infusion should be assessed and treated symptomatically as needed. If severe allergic or anaphylactic-type reactions occur, the administration of Replagal should be discontinued immediately and appropriate treatment initiated. The current medical standards for emergency treatment are to be observed.

Patients experiencing a recurrent IRAE may be premedicated. Pretreatment, generally with oral antihistamines and corticosteroids, from 1 to 3 hours prior to infusion has prevented subsequent reactions in those cases where symptomatic treatment was required. If infusions continue without incident, then tapering of medications can be considered.

6.12 Pregnancy

The sponsor must be notified in the event of a pregnancy occurring during the course of the study and through 30 days after the patient's last dose of study drug. Pregnancy is not to be reported as an AE; the pregnancy form should be used to report the pregnancy. The pregnancy will be followed through delivery or final outcome.

6.13 Removal of Patients from the Study

Patients may withdraw from the treatment protocol at any time. The investigator or sponsor may withdraw a patient from the treatment protocol for the following medical or administrative reasons:

- Adverse event: If a patient experiences an AE that, in the judgment of the investigator, the sponsor, or the Shire medical monitor, presents an unacceptable consequence or risk to the patient, the patient will be withdrawn from the treatment protocol.
- Adverse laboratory experience: If a patient has an adverse laboratory experience that, in the judgment of the investigator, the sponsor, or the Shire medical monitor, presents an unacceptable consequence or risk to the patient, the patient will be withdrawn from the treatment protocol.
- Comorbidity: If a patient develops a comorbidity during the course of the treatment protocol that is not associated with the condition under study, and that requires treatment that is not consistent with protocol requirements, the patient will be withdrawn from the treatment protocol. A patient will be withdrawn from the treatment protocol if, in the judgment of the investigator, he or she develops an intercurrent illness that, in any way, justifies his or her withdrawal.
- Refusal of treatment: If for any reason the patient refuses treatment during the treatment protocol, the patient will be withdrawn from the treatment protocol, and the reason for refusal will be documented on the CRF. Reasonable efforts will be made to monitor the patient for AEs following such discontinuation. Such efforts will be documented in the CRF.
- Withdrawal of informed consent: A patient may withdraw his or her informed consent to participate in the treatment protocol at any time and for any reason.
- Lack of efficacy: The patient will be withdrawn from the treatment protocol if, in the opinion of the CFDI investigator, a lack of efficacy is observed.

At the time of discontinuation or withdrawal, patients will undergo all safety evaluations required for the end-of-study (EOS) visit. The investigator will complete the appropriate eCRF describing the reason for discontinuation.

In addition, patients who withdraw or are discontinued will have a follow-up assessment for safety at the clinical site 30 days after their last infusion of Replagal.

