Appendix 1 Schedule of Events for Cohort 1 (EOW Replagal Dosing Regimen)

Evaluation	Within 6 Months Prior to First Dose	Treatment Period		End of Study (30 Days after Last Dose)
		Dosing Every Other Week (± 5 days)	Biannual/Annual Visits to Site ^a	
Informed Consent	X			
Treatment Protocol Entry Criteria	X			
Medical History	X			
Demographics	X			
Disease and Treatment History	X			
Physical Examination ^b	X		X	
Height ^c and Weight	X ^d		X	
Vital Signs ^e		X	X	
Blood Tests ^f	X		X	
Serum Anti-agalsidase alfa Antibody	X		X	
Drug Administration		X	X	
AE Assessment		X	X	X

Abbreviations: AE=adverse event; CFDI=Canadian Fabry Disease Initiative; EOW=every other week

^a Biannual or annual visits, as applicable, are intended to coincide with visits in the CFDI protocol. Procedures and study assessments during these visits will be performed at the clinical site. For patients receiving home infusions, the infusions given at the biannual or annual visits may be administered at the clinical site.

^b Physical examination includes assessments of head, neck, and thyroid; eyes, ears, nose, and throat; chest and lungs; heart; lymph nodes; abdomen; anorectal; genitourinary; skin; musculoskeletal; endocrine; neurological; and other.

^c Height is measured at baseline for all patients and for patients <18 years at baseline, height will also be measured at biannual or annual safety visits until they are ≥ 18 years of age.

^d Subject weight should be obtained within 1 month prior to the first infusion.

^e Include blood pressure, pulse, respiratory rate, and temperature. Vital signs are taken immediately before and immediately after every infusion (± 10 minutes).

^f Includes creatinine, glucose, urea, potassium, sodium, chloride, bicarbonate, and fasting lipids profile.

Appendix 2 Schedule of Events for Cohort 2 (Weekly Replagal Dosing Regimen for Patients Who Participated in REP001a)

Evaluation	Within 6 Months Prior to First Dose	Treatment Period		End of Study (30 Days after Last Dose)
		Dosing Every Week (± 2 days)	Biannual/Annual Visits to Site ^a	
Informed Consent	X			
Treatment Protocol Entry Criteria	X			
Medical History	X			
Demographics	X			
Disease and Treatment History	X			
Physical Examination ^b	X		X	
Height ^c and Weight	X ^d		X	
Vital Signs ^e		X	X	
Blood Tests ^f	X		X	
Serum Anti-agalsidase alfa Antibody	X		X	
Drug Administration		X	X	
AE Assessment		X	X	X

Abbreviations: AE=adverse event; CFDI=Canadian Fabry Disease Initiative

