5.7.2 Clinical Laboratory Evaluations

Blood will be collected within 6 months prior to the patient receiving the first dose of Replagal and at the biannual/annual safety visits for the following assessments: creatinine, glucose, blood urea nitrogen (BUN), potassium, sodium, chloride, bicarbonate, and fasting lipids profile (total cholesterol, HDL cholesterol, LDL cholesterol, and triglycerides).

The observed values and change from baseline will be summarized by biannual visit for laboratory data using descriptive statistics. Shift tables will also be presented comparing the baseline values to those at each biannual visit. Shifts over time will be presented by low, normal, and high. The numbers (and percentages) of patients within each category will be tabulated. Lab assessments will be summarized by cohort, previous ERT status and overall based on the safety population.

Any patient, who had a clinically significant abnormal value, as determined by the investigator, will be listed.

All laboratory data from both scheduled and unscheduled (i.e., unexpected) visits will be presented in the data listings for the safety population. However, for the summary tables only laboratory data associated with scheduled visits will be summarized.

If there are repeated or retest laboratory measurements associated with a given study visit then, in general, the second set of measurements with respect to date/time order, will be used for the statistical analysis unless the values are invalid or missing. In this instance a value from the first set of measurements will be used provided it is valid and non-missing.

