7.2 Handling of Dropouts or Missing data

Missing values will not be imputed with the exception of analyses involving partial dates and the data obtained at early termination visits.

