Appendix 1 Schedule of Events for Cohort 1 (EOW Replagal Dosing Regimen)

Evaluation	Within 6 Months Prior to First Dose	Treatment Period		End of Study (30 days after last dose)
		Dosing Every Other Week (± 5 days)	Biannual/Annual Visits to Site ^a	
Informed Consent	X			
Treatment Protocol Entry Criteria	X			
Medical History	X			
Demographics	X			
Disease and Treatment History	X			
Physical Examination ^b	X		X	
Height ^f and Weight	X ^e		X	
Vital Signs ^c		X	X	
Blood Tests ^d	X		X	
Serum Anti-agalsidase alfa Antibody	X		X	
Drug Administration		X	X	
AE Assessment		X	X	X

Abbreviations: AE = adverse event; CFDI = Canadian Fabry Disease Initiative; EOW=every other week

^a Biannual or annual visits, as applicable, are intended to coincide with visits in the Canadian Fabry Disease Initiative (CFDI) protocol. Procedures and study assessments during these visits will be performed at the clinical site. For patients receiving home infusions, the infusions given at the biannual visits may be administered at the clinical site.

^b Physical examination includes assessments of head, neck, and thyroid; eyes, ears, nose, and throat; chest and lungs; heart; lymph nodes; abdomen; anorectal; genitourinary; skin; musculoskeletal; endocrine; neurological; and other.

^c Include blood pressure, pulse, respiratory rate, and temperature. Vitals signs are taken immediately before and immediately after every infusion (± 10 minutes).

^d Includes creatinine, glucose, urea, potassium, sodium, chloride, bicarbonate and fasting lipids profile.

^e Subject weight should be obtained within 1 month prior to the first infusion

^f Height measured at baseline for all patients, and for patients <18 years at baseline height will also be measured at biannual safety visits until they are ≥ 18 years of age.

Appendix 2 Schedule of Events for Cohort 2 (Weekly Replagal Dosing Regimen for Patients who Participated in REP001a)

Evaluation	Within 6 Months Prior to First Dose	Treatment Period		End of Study (30 days after last dose)
		Dosing Every Week (± 2 days)	Biannual/Annual Visits to Site ^a	
Informed Consent	X			
Treatment Protocol Entry Criteria	X			
Medical History	X			
Demographics	X			
Disease and Treatment History	X			
Physical Examination ^b	X		X	
Height ^f and Weight	X ^c		X	
Vital Signs ^c		X	X	
Blood Tests ^d	X		X	
Serum Anti-agalsidase alfa Antibody	X		X	
Drug Administration		X	X	
AE Assessment		X	X	X

Abbreviations: AE = adverse event; CFDI = Canadian Fabry Disease Initiative

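### The end-of-study column requires only adverse event assessment at withdrawal, the SAP has no rule for early-termination data, and patients with no post-baseline antibody sample can be counted as antibody-negative

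*Protocol*

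**What the plan says.** Protocol 6.13 describes two contacts for a patient who leaves. At the time of withdrawal, "patients will undergo all safety evaluations required for the end-of-study (EOS) visit". In addition, such patients "will have a follow-up assessment for safety at the clinical site 30 days after their last infusion of Replagal".

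Protocol Appendices 1 and 2 have a single closing column, headed "End of Study (30 Days after Last Dose". Its only mark is on the adverse event row. The SAP's own schedules repeat this under "End of Study (30 days after last dose". The text sections agree with the schedules. Protocol 6.7 places blood collection before first dose and "at the biannual or annual safety visits for the following assessments: creatinine, glucose, urea, potassium, sodium, chloride, bicarbonate, and fasting lipids profile". Protocol 6.8 gives the same timing for antibody samples. Neither section names withdrawal or end of study.

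Four SAP sections bear on the point:

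- **5.7.2 (laboratory):** scheduled and unscheduled results are all listed, and so is any patient with a value the investigator judges clinically significant. However, "for the summary tables only laboratory data associated with scheduled visits will be summarized".
- **5.7.3 (vital signs):** plans a comparison of baseline with values taken after an infusion at the end-of-study visit.
- **7.2 (missing data):** nothing is imputed, except for partial dates and "the data obtained at early termination visits". No method follows.
- **5.6.3 (subgroups):** anti-drug antibody (ADA) or neutralizing antibody (NAb) positive means one or more positive tests in the study evaluation period, and negative means none. There is no third category. SAP 5.7.1 tabulates infusion-related reactions by these groups.

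**The concern.** The Synopsis names vital signs, blood tests and antibodies as safety endpoints followed throughout the study. A reader of Protocol 6.13 would expect a full set of them when a patient stops. The schedule requires none of them at that point, and the withdrawal evaluation has no column of its own. Sites cannot tell what to collect, and programmers cannot tell where to put what is collected.

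Two results are at stake. The first is the laboratory summary and shift tables, which may leave out values taken because a patient was stopping. The second is the table of infusion-related reactions by antibody status. A patient with a negative baseline who reacts early and leaves before the first safety visit enters that table as a reaction in an antibody-negative patient, although no on-treatment sample was tested. That blurs any association between antibodies and reactions.

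**Working it through.** **1. The plan's one design figure.** SAP 3.6 gives at least a 95% chance of seeing one or more events of 5% frequency in 60 patients. 1 − 0.95^60 = 0.9539, so it reproduces. The point does not rest on it, but it serves as a bound in step 5.

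**2. What is required at withdrawal.**

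| Assessment | Biannual/annual visit | End-of-study column (30 days) |
|---|---|---|
| Vital signs | marked | not marked |
| Blood tests | marked | not marked |
| Antibody sample | marked | not marked |
| Adverse events | marked | marked |

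Protocol 6.13 imports whatever the end-of-study visit requires, and that is adverse event assessment only. The column is dated 30 days after last dose, which matches the second contact in 6.13 and not the first. SAP 5.7.3 needs an infusion and vital signs at a visit where the schedule has neither.

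**3. Where a withdrawal sample would go, if one were taken.**

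- *Laboratory:* always in the listings. It enters the summary and shift tables only if the withdrawal visit counts as scheduled, which the SAP does not settle.
- *Antibody:* SAP 5.7.5 has no scheduled-visits rule and lists all antibody data. A positive result would count toward status under 5.6.3 and, as worded, in the overall tabulation. It has no by-visit row unless mapped to a biannual visit.

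**4. Age of the last scheduled sample at withdrawal.** Visit interval L = 6 or 12 months.

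- After at least one safety visit: up to L, so 6 or 12 months. If withdrawal is uniform between visits (an assumption), the mean is L/2, so 3 or 6 months.
- Before the first safety visit, the only sample is the baseline, which may precede first dose by up to 6 months. If the first visit falls L months after first dose (an assumption), the bound is 6 + 6 = 12 or 6 + 12 = 18 months, and there is no on-treatment value.

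**5. Number of patients.** The documents give no withdrawal rate. For an assumed 5% to 30%:

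- 60 × 0.05 = 3 to 60 × 0.30 = 18 patients
- 200 × 0.05 = 10 to 200 × 0.30 = 60 patients

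These are patients with no required laboratory or antibody sample at withdrawal. Those touched by the negative-status rule are the subset who leave before any post-baseline sample.

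As a worst case, suppose these patients gave no laboratory data at all. The chance of seeing a 5% laboratory event from 60 enrolled would fall from 0.954 to 1 − 0.95^57 = 0.946 (5% withdrawal) or 1 − 0.95^42 = 0.884 (30%). The true loss is smaller, because their earlier scheduled results stay in the tables.

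**6. The antibody rule.** A patient negative at baseline, with one infusion, a reaction and no later sample, has no positive test and is therefore negative under 5.6.3. In the 5.7.5 shift tables the same patient's later visits would be Not Available. The two sections treat one patient in two ways.

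**The case against.** A reader might infer that the SAP discards laboratory results taken at withdrawal, so that they are missing from the results. The documents do not support that. SAP 5.7.2 keeps scheduled and unscheduled results in the listings and separately lists clinically significant values. Whether a withdrawal visit is unscheduled at all is open, since the SAP glosses that word as unexpected and Protocol 6.13 requires the evaluation. Nor does the laboratory rule reach antibodies.

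A reader might also infer that the summaries describe only patients who tolerated treatment. That does not follow. Patients who leave stay in the safety population, and their earlier scheduled results stay in the tables. Adverse events leading to discontinuation and infusion-related reactions are tabulated. A laboratory result that triggered withdrawal already exists and can be an adverse event under Protocol 6.10.1.1. Vital signs are taken around every infusion, so a patient who stops after a reaction should have them from that infusion.

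Two further objections carry weight. Adding blood draws at withdrawal would be a new procedure, needing an amendment, central antibody testing and consent that some leavers will have withdrawn. The study is also descriptive, and Protocol 7.5 says only that a blood-test summary table may be produced.

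On antibody status, the study evaluation period is undefined, so a positive baseline may count and keep a patient out of the negative group. That narrows the problem to patients without such a result. It does not remove it.

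What remains is the mismatch between 6.13 and the schedules, the missing early-termination rule, and the wording of negative status.

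**Conclusion.** The point holds in a limited form. As written, withdrawal requires no laboratory, antibody or vital-sign assessment beyond those tied to an infusion or safety visit on that day. Laboratory results taken then may appear only in listings. Two SAP sections presuppose end-of-study or early-termination data that the schedule does not provide. Separately, absence of a positive test is read as a negative result in the reaction-by-antibody table.

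The size is modest and cannot be fixed from the documents. Under the assumed 5% to 30% withdrawal, 3 to 18 of 60 or 10 to 60 of 200 patients have a last scheduled on-treatment sample up to 6 or 12 months old, or none. Fewer are misclassified on antibody status, but early reactors are the cases that matter in that table. The SAP changes are worth making. Whether to add sampling at withdrawal is a design decision that this point does not settle.

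**What to change.** **SAP, with no new data:**

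1. In 5.6.3, require at least one valid post-baseline antibody result for negative status. Class patients with neither that nor a positive test as Not Available, as the 5.7.5 shift tables already do. Say what the study evaluation period covers. For NAb, let a valid ADA-negative result suffice, because only confirmed ADA-positive samples go on to the neutralization assay.
2. In 5.7.2, add a last on-study value row and a baseline-to-last shift table that include early-termination and unscheduled samples.
3. In 7.2, state how early-termination visits map to analysis visits, and complete or delete the imputation exception.
4. In 5.7.3, align the end-of-study vital-sign analysis with the schedule.

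**Protocol:** reconcile 6.13 with Appendices 1 and 2 by stating which existing assessments apply at withdrawal and which at the 30-day follow-up.

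The cost is SAP wording, one extra table and a slightly smaller denominator for antibody-negative patients. The protocol clarification needs an amendment but no new procedure, unless the sponsor chooses to add sampling.
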